4.5 Treatment Start Time

Preoperatively: Patients scheduled for Monday-Thursday surgery will begin treatment 24-48 hours after surgery. Patients scheduled for Monday-Thursday surgery that remain in the hospital longer than 24-48 hours for recovery will begin their treatment the night they return home. Patients scheduled for Friday and Saturday surgery may have their registration completed on Monday to begin treatment Tuesday night. Pharmacy will express deliver the medication to the patient's home if they have been discharged.

Postoperatively: Patients that consent in clinic up to 6 weeks postoperatively will begin taking their medication 24-48 hours after being registered and randomized in clinic.

5.0 THERAPEUTIC/DIAGNOSTIC AGENTS

Sildenafil citrate is a PDE5 inhibitor manufactured by Pfizer, who will supply the medication as well as its placebo. This medication will be maintained by the MSK pharmacy.

Each site will receive a stipend for the purchase of the intracavernosal vasoactive agent trimix combination. This agent is composed of 3 medications: Papaverine 30 mg/mL, Phentholamine

IRB PB

IRB#: 09-005 A(10)

1 mg/mL, Prostaglandin E1 10 mcg/mL. The pharmacy will maintain the supply of injection medication in a refrigerated state.

6.1 CRITERIA FOR SUBJECT ELIGIBILITY

6.2 Subject Inclusion Criteria

- Male, must be \geq 18 years of age, with histologically confirmed prostate adenocarcinoma, that is clinically localized to the prostate gland
- Stable sexual relationship for ≥ 6 months
- Open or laparoscopic bilateral nerve-sparing radical prostatectomy
- Baseline score of ≥ 22 on the International Index of Erectile Function Domain (Appendix A)
- Able to speak, read and write in the English language
- Calculated creatinine clearance (using the 4 variable MDRD equation based on serum creatinine, age, race, and gender) of > 60 cc/min
- Patient is able to walk up two flights of stairs briskly without chest pain
- Patient needs to have their baseline sitting AND standing blood pressure and pulse done at the time of consent

6.3 Subject Exclusion Criteria

- Preoperative or planned postoperative pelvic radiation therapy
- Preoperative or planned postoperative androgen deprivation
- Presence of Peyronie's disease at baseline
- Presence of a penile prosthesis at baseline
- Resection of one or both nerve bundles at surgery
- Any contraindications to sildenafil:
 - o Patient is currently using nitrates;
 - o Presence of retinitis pigmentosa;
 - o Presence macular degeneration;
 - MI or CVA within 3 months;
 - o Patient is currently using MAOI medications
- Patient is taking using alpha blockers
- Patient is taking potent inhibitor of cytochrome P450 CYP3A4 (e.g., Ketoconozole)
- Patient has hepatic impairment
- Patient has history of substance or alcohol abuse
- Patient is currently using penile self injection medication (Trimix, Bimix, or PGE-1)
- Patient requiring sildenafil for penetration
- Use of sildenafil within 30 days of consent

IRB PB

IRB#: 09-005 A(10)

7.1 RECRUITMENT PLAN (WITH LIMITED WAIVER OF AUTHORIZATION)

Potential research subjects will be identified by a member of the patient's treatment team, the protocol investigator, or research team at Memorial Sloan-Kettering Cancer Center (MSKCC). If the investigator is a member of the treatment team, s/he will screen their patient's medical records for suitable research study participants and discuss the study and their potential for enrolling in the research study. Potential subjects contacted by their treating physician will be referred to the investigator/research staff of the study.

The principal investigator may also screen the medical records of patients with whom they do not have a treatment relationship for the limited purpose of identifying patients who would be eligible to enroll in the study and to record appropriate contact information in order to approach these patients regarding the possibility of enrolling in the study.

During the initial conversation between the investigator/research staff and the patient, the patient may be asked to provide certain health information that is necessary to the recruitment and enrollment process. The investigator/research staff may also review portions of their medical records at MSKCC in order to further assess eligibility. They will use the information provided by the patient and/or medical record to confirm that the patient is eligible and to contact the patient regarding study enrollment. If the patient turns out to be ineligible for the research study, the research staff will destroy all information collected on the patient during the initial conversation and medical records review, except for any information that must be maintained for screening log purposes.

In most cases, the initial contact with the prospective subject will be conducted either by the treatment team, investigator or the research staff working in consultation with the treatment team. The recruitment process outlined presents no more than minimal risk to the privacy of the patients who are screened and minimal PHI will be maintained as part of a screening log. For these reasons, we seek a (partial) limited waiver of authorization for the purposes of (1) reviewing medical records to identify potential research subjects and obtain information relevant to the enrollment process; (2) conversing with patients regarding possible enrollment; (3) handling of PHI contained within those records and provided by the potential subjects; and (4) maintaining information in a screening log of patients approached (if applicable).

A total of 200 patients will be enrolled. Given that MSK does approximately 850 radical prostatectomies annually, we estimate that it will take approximately 18 months to 24 months to complete enrollment. Given the baseline erectile function of the general radical prostatectomy population, it is likely that approximately 50% of patients will be eligible.

Patients scheduled for nerve-sparing open or laparoscopic RP will be advised of the study. Those expressing interest will be screened. If eligible, they will be randomized (see Section 14.0) to one of the three arms in a 1:2:2 ratio.

(RB PB

IRB#: 09-005 A(10)

8.0 PRETREATMENT EVALUATION

After subjects are assessed for baseline inclusion and exclusion criteria, eligible patients will be approached. Only patients meeting all pre and post-operative criteria will be included. Patients will complete the IIEF (Appendix A) preoperatively if they consent before surgery or retrospectively if they consent after surgery, and must have a score of ≥ 22 on the Erectile Function Domain. Patients will have standard blood and urine tests to check the function of their organs (e.g. kidney, liver). Patients will also have a sitting and standing blood pressure and pulse done.

Preoperative consent: Patients will be registered as pending on the day of consent.

Postoperative consent: Patients will be registered if they consent within 6 weeks after surgery.

After registration, subjects will be randomized into one of the three previously described study groups and instructed accordingly. Patients will be given a pill diary/sexual encounter diary (Appendix B), drug accountability (Appendix E), and patient instructions sheet (Appendix F). Patients will be given enough diaries to capture all study medication use and at least 18 sexual attempts.

9.0 TREATMENT/INTERVENTION PLAN

Patients will be randomized into one of 3 arms as described above, and will be followed up for 24 months. Patients will be encouraged to have sexual relations, when comfortable after RP. This is 'usual care'. The use of nightly sildenafil citrate and intracavernosal injection therapy is considered investigational, and this study is designed to define whether one, or the other, or a combination of these strategies, should become 'usual care'. Patients routinely complete questionnaires after surgery, the only additional requirement for patients will be the completion of a pill diary/sexual encounter diary, to delineate the exact utilization of medication for sexual relations as well as document all study medication use. Patients will be followed at 3, 6, 9, 12, 18, and 24 months. Intervention (placebo, sildenafil or injection) will be used for 12 months. Patients will have their sildenafil dose adjusted according to their erectile response and side effects (listed in section 11.0). For example, for men responding robustly to sildenafil 100 mg may be down-titrated to 50 mg or 25 mg. Likewise, men who have side effects (as outlined in Section 11.0) at sildenafil 100 mg will be down-titrated to 50 mg or 25 mg. If patients are experiencing side effects from daily 50 mg dose, they may downtitrated to 25mg, by halving the pill. Intra-cavernosal injection agent dose will be downtitrated for penetration hardness erection lasting for greater than 60 minutes or if any side effects are seen, as listed in section 11.0. Trimix and Bimix have a 1 month expiration date. Combination Therapy Arm patients will be prescribed a total of 3 vials of Trimix or Bimix at their 2nd injection training visit and 3, 6, and 9 month protocol visits. The patient will pick up 1 vial after their appointment and outpatient pharmacy will arrange to have the remaining 2 vials shipped to the patient at 1 month intervals to cover their treatment plan for a total of 3 months.

IRB PB

IRB#: 09-005 A(10)

10.0 EVALUATION DURING TREATMENT/INTERVENTION

Before treatment (baseline) and 3, 6, 9, 12, 18, and 24 months visits, patients will be evaluated in clinic. Patients will be asked for any adverse events, since last visit, and will be given the International Index of Erectile Function (IIEF) validated questionnaire (Appendix A), pill diary/sexual encounter diary (Appendix B), and drug accountability (Appendix E). The pill diary/sexual encounter diary (Appendix B) and drug accountability (Appendix E) will be completed at home. Patients will be given enough diaries to capture at least 18 sexual attempts. At each study visit, the paperwork will be collected and the patient given new diaries. The assigned research professional will review paperwork for any mistakes or inconsistencies before patient leaves clinic. Patient's liver functions will be tested and sitting and standing blood pressure, and pulse will be completed at 3, 6, 9, 12, 18, and 24 months visits.

The IIEF is the gold standard questionnaire in erectile function assessment. It has been validated in numerous languages and has been used for more than a decade now in this field. It has 5 domains, one of which is erectile function (the others are libido, orgasm, intercourse satisfaction and overall satisfaction). Each question is scored on a 5 point scale, where '5' is 'always' and '1' is 'never' and '3' is 'half the time', in response to questions pertaining to obtaining and maintaining erection. The pill diary/sexual encounter diary will ask patients to record sexual encounters, whether sildenafil or penile injections was used, at what dose, whether vaginal penetration occurred, and how they rate their erectile rigidity as well as all study medication use.

At 12 months, patients will be instructed to discontinue treatment (that is, either daily pill use or injection therapy). They will be permitted to use PRN sildenafil or injections for the purpose of sexual relations, prescribed through treating physician. Follow up will continue for 24 months in total. The administration of the study medications will be monitored by the research pharmacy staff to ensure compliance with the protocol, as well as maximizing patient safety.

11.1 TOXICITIES/SIDE EFFECTS

The side effects from each pharmacologic intervention are listed below. Side effects will be assessed at each follow-up visit by direct questioning of patients.

Sildenafil:

- 1. Headache 15%
- 2. Flushing of the face 10%
- 3. Gastrointestinal upset 7%
- 4. Temporary visual changes 2%
- 5. Nasal congestion 4%.

(RB PB

IRB#: 09-005 A(10)

Trimix and Bimix:

- 1. PGE1 can induce pain (in up to 30% of patients taking PGE1)
- 2. Fibrotic reactions (i.e. subcutaneous nodules, intracavernosal fibrotic areas, have been reported). In most cases, penile nodules that occur with injection therapy disappear within a few months of stopping.
- 3. Ecchymosis
- 4. Priapism (0.5-5%). (If not treated right away, permanent damage to the penis could occur). Of note, the incidence of priapism in [name] practice is less than 0.15%.

12.0 CRITERIA FOR THERAPEUTIC RESPONSE/OUTCOME ASSESSMENT

Patient outcome will be assessed by the IIEF (International Index of Erectile Function). Therapeutic response will be evaluated by comparing the IIEF score for patients in each treatment arm at each time point.

13.0 CRITERIA FOR REMOVAL FROM STUDY

Sildenafil will be stopped should any significant side effects occur or should the patient require the use of organic nitrate medications.

Intracavernosal injections will be stopped if the patient develops any fibrotic reactions on the penis (except Peyronie's disease).

The patient can also be removed from this study if they chose to withdraw or the study doctor decides it is in the patient's best interest to remove them from the study if these options are appropriate.

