4.4 Intervention

Three interventions are to be used:

1. PRN Sildenafil Arm: Patients will be instructed to take placebo QHS (blinded) except on nights that they are interested in sexual relations, they will then be instructed to use sildenafil 100 mg (open-label) and skip the placebo dose. Placebo will start within 24-48 hours after registration. There will be 40 patients in this group.

(RB PB

IRB#: 09-005 A(10)

- 2. Nightly Sildenafil Arm: Patients will be instructed to take sildenafil 50 mg QHS (blinded) except on nights that they are interested in sexual relations, they will then be instructed to use sildenafil 100 mg (open-label) and skip the 50 mg dose. Sildenafil treatment will start within 24-48 hours post-surgery. There will be 80 patients in this group.
- 3. Combination Therapy Arm: Trimix combination (Papavarine 30 mg/mL, Phentholamine 1 mg/mL, Prostaglandin E1 10 mcg/mL), at initial dose of 5 units (0.05 mL) will be given; the first 2 injections will be done in the MSKCC urology outpatient clinic (if needed, the investigator can determine appropriate amount of injections for patient training). The patients will be instructed, by the sexual medicine nurse practitioner, on the technique of injection and dose titration, as well as the limitations, contra-indications, side effects and alternatives. The dosing data will be entered into electronic medical record or patient medical record by the NP. The dose being used cannot be altered by a patient. For safety reasons all dose adjustments are conducted by phone with the NP.

For the first 2 weeks after registration, patients will use nightly sildenafil 50 mg before commencing penile injections 2 weeks (± 3 days) later. Sildenafil treatment will start within 24-48 hours after registration. Patients will inject three times per week and use sildenafil 50 mg on the other four nights. In this arm, patients will be instructed to obtain 3 penetration hardness ($\geq 60\%$ rigidity) erections per week. There will be 80 patients in this group.

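### Section 9 lowers the injection dose for fibrotic reactions, while Section 13 stops injections for the same event; Section 9 needs a one-clause exception

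*Combined protocol and SAP*

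**What the plan says.** Three sections of the protocol bear on the point.

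- **Section 9 (treatment plan).** "Intra-cavernosal injection agent dose will be downtitrated" when a penetration-hardness erection lasts more than 60 minutes, "or if any side effects are seen, as listed in section 11.0".
- **Section 11 (toxicities).** The list for Trimix and Bimix has four items: pain, fibrotic reactions, ecchymosis and priapism. Under fibrotic reactions it states that "subcutaneous nodules, intracavernosal fibrotic areas, have been reported". It adds: "In most cases, penile nodules that occur with injection therapy disappear within a few months of stopping".
- **Section 13 (removal criteria).** "Intracavernosal injections will be stopped if the patient develops any fibrotic reactions on the penis". A parenthesis exempts Peyronie's disease.

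Section 4.4 adds how dose changes are made: "For safety reasons all dose adjustments are conducted by phone with the NP".

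**The concern.** The same clinical finding leads to two different instructions. A nurse practitioner working from the dosing paragraph in Section 9 would lower the dose and let the man go on injecting. One working from Section 13 would stop the injections. The difference matters to the man, because the protocol's own statement about resolution of nodules refers to stopping. It says nothing comparable about a lower dose. At stake is consistent and safe handling of fibrosis in the combination arm.

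**Working it through.** The plan states no figure on this point, so the check is a comparison of the rules.

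1. **What triggers Section 9.** A prolonged erection, or any side effect in the Section 11 list. Neither Section 9 nor Section 11 excludes any item, so fibrotic reactions are included.
2. **What triggers Section 13.** Any penile fibrotic reaction other than Peyronie's disease.
3. **Where the two overlap.** Subcutaneous nodules and intracavernosal fibrotic areas that are not Peyronie's disease. The Peyronie's exception narrows the overlap but does not remove it.
4. **Whether both actions can be carried out.** They cannot. Lowering a dose presupposes that injections continue; stopping ends them. Section 13 is met once any such reaction develops, so it leaves no room for a trial period at a lower dose.
5. **Whether the protocol ranks the rules.** Sections 4.4, 9, 10, 11 and 13 contain no statement of precedence, and Section 9 does not refer to Section 13.
6. **Which rule should prevail.** Section 13. It names the event, whereas Section 9 takes it in only through a general reference to a list. Section 11 points the same way, because it describes nodules resolving after injections stop.
7. **How far the conflict extends.** Of the four listed items, only fibrotic reactions have an injection-specific stopping rule in Section 13. For pain, ecchymosis and priapism that section names no stop, so an exception for one item removes the conflict.

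**Reach.** The injection rules concern the combination arm, planned at 80 men. Section 11 gives rates for pain (up to 30% of patients taking PGE1) and priapism (0.5-5%) but none for fibrotic reactions. The number of men who would meet both rules cannot be computed from the documents.

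**The case against.** The strongest reply is that the conflict resolves itself. Section 9 is a general titration sentence, Section 13 is a dedicated stopping rule for the exact event, and a careful clinician would apply the specific rule. Section 13 also lets the study doctor withdraw a man in his best interest. This stands as a reason to think harm unlikely and to grade the point as minor. It does not correct Section 9, which uses an unqualified reference to the whole list and is where staff would look when adjusting a dose.

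A reader might infer three stronger points that the documents do not support.

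- **That fibrosis would go undetected because no penile examination is scheduled.** None is named in the text available, and Section 11 says "Side effects will be assessed at each follow-up visit by direct questioning of patients". But Section 10 also has men evaluated in clinic at each visit, Section 4.4 has side effects taught to them, and new vials are prescribed "at their 2nd injection training visit and 3, 6, and 9 month protocol visits". The patient handout, adverse event form and instruction sheets (Appendices C, D and F) are listed but not available here and may say more. Scheduled palpation in this arm alone would also make detection of lesions unequal between arms.
- **That a stated number of excess injections follows.** At three per week, with visits nominally 13 weeks apart and a window of ±2 weeks at each visit, the interval is 9 to 17 weeks, or 9 × 3 = 27 to 17 × 3 = 51 injections. That is calendar arithmetic. Without a rate of fibrosis or of missed lesions it does not measure harm.
- **That handling by phone makes the error likely.** Section 4.4 presents the phone rule as a safeguard, and a stop under Section 13 is not a dose adjustment.

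**Conclusion.** The concern holds as an inconsistency between two operative safety rules. For a fibrotic reaction other than Peyronie's disease, Section 9 directs a lower dose and Section 13 directs a stop, with nothing to rank them. Section 13 should govern, and Section 9 is wrong as written.

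The point is minor and concerns participant safety only. It does not touch the sample size, the IIEF erectile function score at 24 months, or the intention-to-treat analysis, which keeps men in their randomized groups whatever treatment they receive. The conclusion rests on the wording of the protocol body alone and assumes no rate of fibrosis. Text in the unavailable appendices might guide staff to the right action, but the two sections would still disagree.

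**What to change.** In Section 9, directly after the reference to the Section 11 list, add: *except fibrotic reactions, for which injections are stopped (Section 13)*. The cross-reference brings in Section 13 as it stands, including its Peyronie's exception.

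The cost is one clause in an amendment. There is no new visit, examination or data item, and no change to the sample size or analysis. If the patient instruction sheets or handout repeat the dose-reduction rule, the same clause should be added there.

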14.1 BIOSTATISTICS

14.2 Sample Size

For each endpoint we will conduct three analysis:

- 1. A comparison of nightly sildenafil to PRN sildenafil with an alpha of 2.5%
- 2. A comparison of combination treatment to PRN sildenafil with an alpha of 2.5%
- 3. A non-inferiority comparison between nightly sildenafil and combination treatment: in this analysis, nightly sildenafil will be considered non-inferior to combination treatment if the upper bound of a 90% confidence interval for the difference between groups does not include combination treatment being at least three points superior to nightly sildenafil.

(RB PB

Amended: 02/12/13

- 15 -

IRB#: 09-005 A(10)

Our rationale is for the different comparisons is as follows. We want to know whether the two active arms (nightly sildenafil and combination treatment) are superior to control (PRN sildenafil). We will therefore test each against control using an alpha half of the conventional value to account for multiple testing. Furthermore, combination treatment, which involves penile injection, is less tolerable for patients than nightly sildenafil, which only involves oral medication. Therefore unless nightly sildenafil is demonstrably inferior to combination treatment, we will recommend that injections are not required. Hence we will conduct a non-inferiority comparison between the two active arms.

Our primary endpoint is the IIEF-EF at 24 months. Based on previous studies, we estimate that the SD for the IIEF-EF will be 9 points. Prior data at MSKCC suggest that the correlation between baseline and follow-up IIEF-EF will be small enough as to have a negligible effect on variance. The minimum, clinically significant difference between active and control arms is 6 points based on our clinical experience and discussion held with [name] the designer of the IIEF. If we obtain data from 80 patients on each of the two active arms (nightly sildenafil and combination therapy) and 40 patients on the control arm (PRN sildenafil), we will have 89% power for the comparison between active and control and 80% power for the non-inferiority comparison between active arms.

MSKCC surgeons do approximately 850 radical prostatectomies per year. We estimate that 50% of patients will be eligible for the study. Assuming that 25% - 33% of eligible patients enroll, we should complete accrual within 18-24 months.

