14.3 Data Analysis

Summary statistics will be calculated, by group, for age, surgery (open or laparoscopic), tumor characteristics (stage, grade, PSA), baseline erectile function and quality of life scores. Compliance and off-study use of medications for erectile function will be described by group and follow-up time. Biochemical recurrences will be described separately by group using Kaplan-Meier methods.

The primary analysis will compare the erectile function domain score of the IIEF at 24 months. Secondary endpoints include:

- 1. EF scores at other time-points
- 2. The proportion of patients who have normalization of their erectile function, defined as a score of 26 or greater on the EF domain of the IIEF at any point during the study
- 3. Time for response to sildenafil (as defined by diary)
- 4. Time to return of spontaneous functional erections (as defined by diary)

(RB PB

IRB#: 09-005 A(10)

The primary comparison and secondary comparison 1 will be made by analysis of covariance with baseline score and randomization strata as the covariates. Secondary endpoint 2 will be compared by Fisher's exact test. Secondary endpoints 3 and 4 will be compared between groups by log rank. Three pairwise comparisons will be made: nightly sildenafil vs. PRN sildenafil; combination treatment vs. PRN sildenafil; nightly sildenafil vs. combination treatment.

As an additional analysis, we will model EF scores over time using Generalized Estimating Equations with time, treatment, time by treatment and baseline score as predictors. Treatment will be entered as two dummy variables: nightly sildenafil (coded 0 in the PRN group and 1 otherwise) and injection therapy (coded 1 in the combination group and 0 otherwise).

All analyses will be on the intention-to-treat principle with patients analyzed in their randomized groups regardless of the treatment actually received. All comparisons between combination and PRN sildenafail, and between nightly and PRN sildenafil, will use a 2.5% alpha; all comparisons between the two treatment arms will use a 90% non-inferiority bound.

The nature, severity and day of onset of adverse effects will be described along with assessment of causality.

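### The fixed 2.5% split for the two active-versus-PRN tests is valid, but Holm's step-down rule would give more power at the same 5% family error rate

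*Combined protocol and SAP*

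**What the plan says.** Section 14.2 (Sample Size) sets three analyses for each endpoint: nightly sildenafil against PRN sildenafil at 2.5%, combination against PRN sildenafil at 2.5%, and a non-inferiority comparison of the two active arms using a 90% confidence interval and a 3-point margin. The reason given for the 2.5% is multiplicity alone: "We will therefore test each against control using an alpha half of the conventional value to account for multiple testing". Half of the conventional value implies a 5% family error rate over the two superiority tests.

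Section 14.3 (Data Analysis) confirms that the level is fixed: "All comparisons between combination and PRN sildenafail, and between nightly and PRN sildenafil, will use a 2.5% alpha". Neither section has a step-down, gatekeeping or alpha-recycling rule.

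The power claim is for one comparison at a time: "we will have 89% power for the comparison between active and control". No power is given for showing both arms superior. The plan does not say whether the 2.5% is one-sided or two-sided.

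**The concern.** Section 14.2 asks whether the two active arms are superior to control, so both superiority tests are of interest. Under a fixed Bonferroni split, the alpha spent on a comparison that has already succeeded is not passed on, and the remaining arm still faces the stricter threshold. Holm's rule passes it on. Any pair of p-values that leads the split to reject also leads Holm to reject, and Holm's family error bound is the same 5% under any dependence between the tests. At stake is some power for the second of the two comparisons, at no cost in patients, visits or data.

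**Working it through.** **Inputs, all from 14.2 unless noted.**
- Difference: "The minimum, clinically significant difference between active and control arms is 6 points".
- SD: "we estimate that the SD for the IIEF-EF will be 9 points".
- Baseline adjustment: the correlation with baseline is taken to be "small enough as to have a negligible effect on variance", so there is no variance reduction.
- Patients with data: 80 nightly, 80 combination, 40 PRN (1:2:2 in the recruitment plan, section 7.1).
- Sidedness: not stated; inferred below.

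**Step 1: reproduce the stated 89%.**
SE of an active-minus-PRN difference = 9 × √(1/40 + 1/80) = 1.743.
Standardised effect = 6 / 1.743 = 3.443.
Two-sided 2.5% critical value = 2.241.
Power = Φ(3.443 − 2.241) = Φ(1.201) = 88.5%, which agrees with 89% (a noncentral t with 118 df gives 87.8%). One-sided 2.5% gives Φ(3.443 − 1.960) = 93.1%, which does not. The plan's 2.5% is therefore read as two-sided.

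**Step 2: correlation of the two tests.** They share the PRN arm, so correlation = (1/40) / (1/40 + 1/80) = 2/3.

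**Step 3: the two rules.**
- Fixed split: reject each comparison if |z| > 2.241.
- Holm: the larger |z| must exceed 2.241; if it does, the other is tested against 1.960.

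Holm's family error is at most 5%. If both nulls hold, an error needs at least one test significant at 2.5%, so the chance is at most 2.5% + 2.5%. If one null holds, its test can never be rejected unless it is significant at 5%.

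**Step 4: results.** Four million simulated pairs of z-statistics, checked by numerical integration of the bivariate normal:

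| True gains (points) | Quantity | Fixed split | Holm |
|---|---|---|---|
| 6 and 6 | Power per comparison | 88.5% | 91.5% |
| 6 and 6 | Both significant | 82.3% | 88.4% |
| 6 and 6 | At least one significant | 94.7% | 94.7% |
| 0 and 0 | Family error | 4.4% | 4.4% |
| 6 and 0 | False positive, ineffective arm | 2.5% | about 4.3% |

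Check on the Holm row: with equal gains, the two per-comparison powers sum to P(at least one) + P(both) = 94.72% + 88.35% = 183.07%, and half of that is 91.5%. The last entry is 4.26% by simulation and 4.25% by integration. As the effect in the other arm grows, it rises towards 5.0% and does not pass it.

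**Step 5: where the rules differ.** They disagree only when one arm has passed 2.241 and the other lies between 1.960 and 2.241. For that arm this is an observed difference between 1.960 × 1.743 = 3.42 and 2.241 × 1.743 = 3.91 points. These are also the cases where the 97.5% interval (half-width 3.91) includes zero although the arm is declared superior.

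**Step 6: the gain in patients.** Under the fixed split at 1:2:2, 44 PRN patients give 91.45% per comparison, just short of Holm's 91.5%; 45 give 92.1%. Matching Holm would take about 45 + 90 + 90 = 225 patients instead of 200.

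**The case against.** The strongest reply is that nothing here is wrong. The split is pre-specified, explained, applied consistently in both sections, and delivers the power claimed for it. That stands, and it limits the point to a suggestion.

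Second, the extra power is bought with error. Equal family error under the global null (4.4% for both rules) could be read as showing that Holm is free. It is not: the false-positive rate for an ineffective arm rises from 2.5% to about 4.3% when the other arm truly gains 6. A team that wants 2.5% per arm for its own sake could keep the split. However, the only reason given in 14.2 is multiplicity at the conventional level, and Holm meets that target.

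Third, the dominance argument could be carried further. A step-down Dunnett test uses the 2/3 correlation, with a first-step critical value of about 2.187, and is slightly more powerful than Holm. True, but it relies on the normal model and the known correlation. Holm needs nothing that the present rule does not already need.

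Fourth, a reader might infer that the second comparison decides whether both regimens can be recommended. The documents do not support this: 14.2 rests the choice between regimens on the non-inferiority comparison, which Holm leaves untouched, and it nowhere requires both arms to beat PRN.

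Fifth, larger gains can be shown with smaller effects: with true gains of 6 and 3, power for the weaker arm goes from 30% to 40%. A 3-point effect is half of what 14.2 calls the minimum clinically significant difference, so this is not a fair measure of what the plan loses.

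**Conclusion.** A cheap improvement, not an error. At the plan's own design values Holm adds 91.5 − 88.5 = 3.0 percentage points of power per comparison and 88.4 − 82.3 = 6.1 points for showing both arms superior. It adds nothing to the chance of at least one significant comparison. A reader might infer that the trial is underpowered or that its type I error is not controlled; neither follows, since the 89% reproduces and the split holds the family error below 5%.

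The power figures assume normal test statistics, SD 9, no gain from baseline adjustment, two-sided testing, and all 200 patients contributing 24-month data. The statement that Holm never rejects less than the split and keeps the family error at or below 5% needs none of these beyond valid p-values. The family here is the two superiority tests within one endpoint; neither rule adjusts across endpoints or covers the non-inferiority comparison.

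**What to change.** In 14.2 and 14.3, replace the fixed 2.5% with this rule, applied separately within each endpoint: test the smaller of the two active-versus-PRN p-values at two-sided 2.5%; if it is significant, test the other at two-sided 5%; if it is not, stop and declare neither. State the two-sidedness explicitly. Leave the non-inferiority comparison as it is, and still report 97.5% confidence intervals for both comparisons with PRN.

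Record the two downsides in the plan: a 97.5% interval may include zero for an arm that wins at the second step, and the false-positive rate for an ineffective arm can exceed 2.5% (about 4.3% when the other arm truly gains 6, never above 5%). The 89% statement can stay, since Holm gives each comparison at least that power.

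The cost is a wording amendment, made before any comparison by arm is seen. No patients, visits or data items change.
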